### Combining Endpoints

We are combining the two endpoints using a utility function framework, which has been discussed from a Bayesian adaptive design point of view. The following describes how we built our utility function. Suppose Drug B has better efficacy than Drug A, but Drug A has a lower quit rate due to tolerability than Drug B. What would the “quit rates” and “efficacies” have to be in order for Drug A to be clinically the same as Drug B? An elicitation tool that looks at various comparisons (seven of them) was created that asked three of the clinical experts on this proposal (i.e. [name], [name], and [name]) to provide the point of equivalency (Table 3).

**Table 3. This table was presented to clinical experts and they were asked to fill in the underlined values, which are filled-in here but were blank when given to the experts.**

Scenario	Drug A			Drug B	
	%Efficacy	%Quit		%Efficacy	%Quit
#1	30%	15%	Equals	40%	30%
#2	30%	5%	Equals	40%	10%
#3	50%	20%	Equals	40%	15%
#4	50%	30%	Equals	40%	20%
#5	30%	15%	Equals	50%	30%
#6	20%	2%	Equals	50%	10%
#7	25%	15%	Equals	50%	35%

We then plotted the points from Table 3 that were considered "equal" and then plotted lines of constant utility. This resulted in identifying that 4 points of efficacy = 3 points of quit rate. This utility function was acceptable to the clinical team. Specifically, the utility function is  $U(E,Q) = .75E + 1 - Q$ .

Combining patient ratings of efficacy with data on the percentage of patients who stop taking the drug to which they were assigned provides us with an important single measure of which drug is 'best.'

### Virtual Participant Response

For the purposes of this investigation we looked at several virtual (or "pretend") responses to determine the power, sample size and time (duration) needed for our study. We created several scenarios for both efficacy and quit rates using five patterns for efficacy and three patterns for quit rates (Table 4). These were then combined into several possible combinations (e.g., one combination would be a 'best' and '2nd best' drug for efficacy and a 'no differences' for quit rate, another might be 'no differences' for efficacy and 'no differences' for quit rate, etc.).

**Table 4. Virtual response patterns for each endpoint.**

	1	2	3	4	
	Efficacy				
No Difference	0.30	0.30	0.30	0.30	all drugs are equally efficacious
Best and 2 nd Best	0.30	0.40	0.50	0.30	one drug is best, one is 2 nd best
All Different	0.40	0.45	0.50	0.30	all have different efficacy
One Strong Best	0.30	0.30	0.50	0.30	one drug is much better
One Modest Best	0.30	0.30	0.40	0.30	one drug is modestly better
	Quit				
No Difference	0.20	0.20	0.20	0.20	all drugs have same quit rates
Positive Relation	0.30	0.25	0.15	0.30	Most efficacious drug has lowest quit rate
Negative Relation	0.20	0.40	0.60	0.20	Most efficacious drug has highest quit rate

NOTE: "Positive" relation refers to both efficacy and quit percentages being good; "Negative" relation refers to either good efficacy and high quit percentages or low efficacy and low quit percentages.

### Accrual (patient enrollment) Patterns

Accrual patterns are important to Bayesian adaptive designs and refer to how rapidly each site enrolls patients in the trial. We assume that the distribution of the accrual patterns follows a Poisson distribution with a mean, or average, number of patients accrued per week. The accrual patterns depend on two factors: (1) the number of sites actively enrolling patients in the trial, and (2) how fast the sites can enroll, which we assume is a constant for each. We expect after a ramp-up of around 8 weeks of enrolling patients, using information from the participating 40 site investigators, we should accrue an average of 4.2 patients/week. Determining this is important for identifying how long the trial will last.

### Statistical Model

Of necessity the following is fairly technical, but it is needed to allow for appropriate statistical review and because it is the statistical model that will evaluate final determination of which drug is "best". This is referred to as the arm of maximum utility (i.e., the drug with the

best combination of patient reported efficacy and percentage of patients who quit taking the drug.) For this study the two endpoints are respectively  $S_{EjT}$  for efficacy and  $S_{QjT}$  for quitting. The number who did not quit and were not efficacious is  $Sn_{EjT}$ . These are modeled as a multinomial distribution  $(S_{QjT}, S_{EjT}, Sn_{EjT}) \sim \text{MultNomial}(\theta_j^q, \theta_j^e, \theta_j^{ne})$ . In addition, we provide “weakly informative” priors,  $(\theta_j^q, \theta_j^e, \theta_j^{ne}) \sim \text{MultNomial}(1/3, 1/3, 1/3)$ . Using the endpoint data and the prior probabilities, we then use Markov Chain Monte Carlo computations to obtain the Bayesian posterior distributions of  $\{\theta_j^e | S_{EjT}\}$  and  $\{\theta_j^q | S_{QjT}\}$  respectively for each endpoint (i.e., efficacy and quitting.)

The utility function previously discussed is used for determining whether we have met our stopping criterion. Specifically, the rule is we will stop the trial if the probability of an arm (i.e., a drug) having maximum utility is greater than 0.925. This may first be determined after enrolling 100 of the 400 potential patients. The utility function is

$$U_{jT} = .75\{\theta_j^e | S_{EjT}\} + 1 - \{\theta_j^q | S_{QjT}\} \text{ and the arm (or drug) having the maximum utility is}$$

$U_{\max,T} = \max(U_{1T}, U_{2T}, U_{3T}, U_{4T}, U_{5T})$ . The stopping rule is mathematically  $P(U_{\max,T}) > .925$ . If a maximum utility arm (drug) is not identified after completed data on 100 patients, this procedure and accrual will continue until a maximum arm is identified or we reach 400 enrolled patients. At the end of the trial we will also decide that an arm is a “loser” if there is a very unlikely chance that it is the best,  $P(U_{\max,T}) < .01$ .

#### Adaptive Randomization: Allocation

After the stopping rule is evaluated the next round of patients are randomized using a formula that takes advantage of the information gained from our analyses up to that point. Using this formula, each arm (or drug) is allocated for the next patients to be enrolled in the  $j^{\text{th}}$

arm proportional to  $V_j^* = \sqrt{\frac{\Pr(U_{jT} = U_{\max,T}) \text{Var}(U_{jT})}{n_{jT} + 1}}$ . This type of allocation tends to have more

desirable properties than simply using  $\Pr(U_{jT} = U_{\max,T})$ . Using this approach will allow us to assign more patients to the most promising arm or drug, and fewer patients to the least promising drug.

#### Longitudinal Model

This model predicts patients 12 week data from data at early time points (4 and 8 weeks). Estimate transition probabilities from outcome at early time point to final outcome. The number of transitions to final outcome given early outcome is distributed as multinomial with the following parameters. If a patient quits treatment early, we transition the patient to quit at 12 weeks. Let p21, p22, and p32 be conditional on a patient showing early efficacy, the respective final probabilities of quit, efficacy, and not efficacy. For these we use a Dirichlet prior on transition probabilities,  $(p21, p22, p32) \sim \text{Dirichlet}(1, 7, 2)$ . Similarly for a patient that shows no efficacy early, the final prior probabilities are  $(p31, p32, p33) \sim \text{Dirichlet}(1, 2, 7)$ . These are fairly diffuse, each having a prior sample size equivalent to ten patients.

We estimate transition probabilities separately for each treatment group and for 4 and 8 week early time points. Here is the algorithm for the longitudinal model. Calculate the posterior probability each treatment is best by:

1. Sample posterior transition probabilities from longitudinal model
2. Impute 12 week data values for patients with at least 4 week values given sampled transition probabilities

3. Sample values from the posterior distribution under each treatment given imputed 12 week data
4. Given each vector calculate the utility under each treatment
5. Report the treatment with the max utility
6. Repeat 1-5 and summarize posterior probability that each treatment is best as the proportion of times it had the max utility.

Here is the longitudinal scenario based on elicitations from the clinical team, which resulted in transition probabilities for evaluating the trial's operating characteristics. To simulate the early outcomes, one first simulates the final outcomes from a multinomial distribution. Then the early outcomes are also multinomial simulations conditional on these final outcomes. Specifically, if the final outcome is a quit, then the probabilities of early quit, efficacy, non-efficacy is 0.80, 0.10, and 0.10 respectively. If the final is effective then we have 0, .67, and .33 respectively. If not effective then is 0, .33, and .67.

### Simulation Algorithm

The following steps summarize the algorithm (or rule) used to determine power, sample size, and duration of the trial. These are all necessary elements for establishing that the trial is of sufficient size and length to yield valid results. For this algorithm we used the "virtual patient responses" parameters (or simulated data) previously discussed. **Step 0:** Set the index for simulation iteration to be  $b=0$ . **Step 1:** Set  $b=b+1$ . **Step 2:** Simulate the initial observed data. **Step 3:** estimate posterior parameters via simulation and calculate the stopping rule and the possible next allocation. **Step 4:** repeat steps 2 and 3 after collecting four more weeks of data. **Step 5:** evaluate all of the data after collecting all of the endpoints. **Step 6:** go to step 1 unless  $b=1000$ , then stop. Initially we used this algorithm in a software package called FACTS™ (Fixed and Adaptive Clinical Trials Simulator). FACTS™ is very powerful and can handle a wide variety of models for exploring the operating characteristics of Bayesian clinical trials designs. It was developed by [name], who co-authored the PCORI methods guidelines and wrote the Bayesian adaptive design portion of those guidelines. [name] is a consultant on this application and the University of Kansas Medical Center is the first academic institution with license to use FACTS™. We then programmed the algorithm in the software R to handle the multinomial case for the simulation and adapted it for use during the actual trial.

### Power, Sample Size, and Trial Duration

We performed several trial simulations based on the various combinations of efficacy (5 types) and quit (3 types) endpoints that were shown in Table 4. We varied the maximal accrual into the study after several weeks and, as previously identified, found 4.2 patients/week to be very close to the optimal combination of sample size and trial duration. These simulations resulted in identifying power (the probability of success) in two components—one for early success (i.e., being able to stop the trial early) and one for late success of the trial (i.e., after enrolling all 400 patients) (see Table 5). While some of these combinations are very unlikely to occur, we include all possible combinations in Table 5, ordered from most to least power. We highlight four scenarios, here.

**First** we want to highlight the unlikely scenario that serves as our null hypothesis (**scenario #1 in Table 6**). In this scenario there are no differences in efficacy or in quit rates among the drugs. Therefore, the extent to which this scenario is "successful" actually reflects our Type I error rate. For this scenario, we estimated (identified) that 5.5% of the simulated trials had early success, .6% late success. Thus this trial scenario produced an appropriate expected Type I error ( $\alpha \sim .05$ ). The sample size of this scenario on average was 393 patients. The average length of the trials under this scenario was 108 weeks. **Second (scenario #2 in**

**Table 6)**, if there is a best drug and second best drug in terms of efficacy and quit rates, we estimated (identified) that 78% of the simulated trials had early success, 2% had late success, and 20% had incomplete results. This trial scenario had 80% power and the sample size of this trial scenario was on average 298. The average length of this trial scenario was 78 weeks.

**Third (scenario #3 in Table 6)**, if there is one strong best drug in terms of efficacy and quit rates, we estimated (identified) that 92% of the simulated trials had early success, 2% late success, and only 6% had incomplete results. Thus this simulation had 94% power. The average sample size of this trial scenario was 266. The average length of these simulated trials was 68 weeks. Close to half of the sample size, 108, was on the best treatment. **Fourth (scenario #4 in Table 6), a very unlikely case, is** if there is one strong best drug in terms of efficacy and but quit rates that are higher for the drug with high efficacy, we estimated (identified) that 10% of the simulated trials had early success, 2% late success, and 88% had incomplete results. Thus this simulation had 12% power. The average sample size of this trial scenario was 387. The average length of these simulated trials was 107 weeks. However, this trial does a decent job correctly identifying treatment 2 as the loser (65%).

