### Bayesian Adaptive Design

Patients will be randomized to one of four treatment arms (groups) with a maximum number of patients  $n_{max}=400$ . Using a Bayesian Adaptive Design, at each interim analysis a decision will be made to either continue enrolling patients or to stop the trial for success. If patient enrollment continues, the randomization structure (i.e., how we randomize patients to each drug) will also be updated. Two endpoints are used to drive the adaptive randomization and stopping criteria. The first endpoint is the percentage of patients who report a 50% or greater decrease on the Likert-type pain scale after 12 weeks. The second endpoint is the percentage of patients that discontinue treatment. After 80 patients are enrolled (see definition of “enrolled” in the consent form section towards the end of this protocol) and equally randomized to the four arms, we begin adapting the randomization. Then, after we have endpoint data on 100 patients, the data will be analyzed (a first interim analysis) and an updated randomization schedule will be used. Specifically, the arm, or drug, that looks to be the best

will get more participants allocated to it in this subsequent randomization. A new adaptive randomization schedule will be updated and an interim analysis will occur every 13 weeks after the first interim analysis, using up to date outcome data, until the trial is stopped (i.e. for early success). Early success stopping criteria will be if the probability of the maximum arm (i.e., the best drug), measured by a combined utility of the pain and treatment discontinuation endpoints, is larger than 0.925. While this will halt new patient enrollment, we will confirm this finding with a subsequent analysis and evaluation after all data from all enrolled patients are obtained as some will still be actively in the study when the early stopping criterion is identified. Also determined is which of the arms are losers, and is defined as an arm that has a probability of being maximum as less than 0.01. This will be a useful result in cases where a best arm could not be identified. If a loser or two is identified then the drug(s) would not be recommended for use in clinical practice.

A summary of the overall general design is as follows.

- Begin a new adaptive randomization schedule once 20 patients have been enrolled on each treatment.

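### Stated mean trial lengths of 78 and 68 weeks omit follow-up after an early stop (about 87 and 79 with it), and stated power does not apply the plan's final-analysis rule

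*Combined protocol and SAP*

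**What the plan says.** All places are in the combined protocol and SAP, part D (Analytic Methods).

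- **Length.** The section on power, sample size and trial duration says of Scenario 2: "The average length of this trial scenario was 78 weeks". Of Scenario 3 it says: "The average length of these simulated trials was 68 weeks". Table 6 repeats both under Mean Trial Weeks, with 108 and 107 for Scenarios 1 and 4.
- **Accrual.** After a ramp-up of around 8 weeks, "we should accrue an average of 4.2 patients/week". The section adds: "Determining this is important for identifying how long the trial will last".
- **Early stop.** Under Bayesian Adaptive Design, a crossing of .925 halts enrolment, and then "we will confirm this finding with a subsequent analysis and evaluation after all data from all enrolled patients are obtained". The bulleted summary that follows calls a treatment best in the final analysis only if its probability of being best exceeds .925.
- **Simulation.** Step 5 is to "evaluate all of the data after collecting all of the endpoints". Step 4 is to "repeat steps 2 and 3 after collecting four more weeks of data". Of power, sample size and duration the section says: "These are all necessary elements for establishing that the trial is of sufficient size and length to yield valid results".
- **Power.** It has two parts: early success, meaning that the trial can stop early, and late success after all 400 are enrolled. Table 6 gives totals of 0.798 (Scenario 2) and 0.939 (Scenario 3).

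**The concern.** An early-stopped trial has no final result until its last enrolled patients reach week 12. The stated lengths for the two favourable scenarios look too short to contain that period. A planner reading 78 and 68 weeks as time to the result would be about two months short or more, and only in the scenarios where the design looks best.

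The success probabilities raise a related question. They are scored at the interim crossing, whereas the plan declares a drug best on complete data. If some early stops fall to .925 or below once follow-up is complete, the chance of a trial that ends with a declared best drug is lower than the stated power. The plan does not say what would be concluded from such a trial.

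**Working it through.** **Duration**

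Inputs: 4.2 patients/week; an 8-week ramp, assumed linear because its shape is not given, which costs 8/2 = 4 weeks of full-rate accrual; a 12-week endpoint; mean N and early-success probability P from Table 6. Results use unrounded values.

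First, reproduce the plan by counting follow-up only in trials that do not stop early: length = 4 + N/4.2 + 12 × (1 − P).

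| Scenario | N | P | N/4.2 | Reproduced | Stated |
|---|---|---|---|---|---|
| 1 | 393 | .055 | 93.6 | 108.9 | 108 |
| 2 | 298 | .777 | 71.0 | 77.6 | 78 |
| 3 | 266 | .923 | 63.3 | 68.3 | 68 |
| 4 | 387 | .103 | 92.1 | 106.9 | 107 |

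All four agree to within a week. Next, count follow-up in every trial:

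- **Floor with no ramp**, N/4.2 + 12: 105.6, 83.0, 75.3, 104.1. Scenarios 2 and 3 already exceed the stated 78 and 68, by 5.0 and 7.3 weeks.
- **Ramp delay implied by the stated lengths**, weeks − 12 − N/4.2: +2.4, −5.0, −7.3, +2.9. A negative delay is impossible. Rounding of the table moves the two negative values only to −5.6 to −4.3 and −8.0 to −6.7. If follow-up is left out after early stops, weeks − 12 × (1 − P) − N/4.2 gives 3.1, 4.4, 3.7, 4.1, close to the 4.0 of a linear ramp.
- **Another accrual rate does not help.** With follow-up in every trial, Scenarios 1 and 3 differ by 108 − 68 = 40 weeks and 393 − 266 = 127 patients. The rate would be 127/40 = 3.2 per week, and the delay about −28 weeks.

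With follow-up added, stated + 12 × P:

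- Scenario 2: 78 + 12 × .777 = 87.3
- Scenario 3: 68 + 12 × .923 = 79.1
- Scenario 1: 108 + 12 × .055 = 108.7
- Scenario 4: 107 + 12 × .103 = 108.2

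**Power**

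Table 6 totals are crossings plus late success: .777 + .021 = .798 and .923 + .016 = .939. The drug-wins columns, although labelled with the .925 rule, add to the same total (Scenario 2: .001 + .797 = .798).

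The design was re-simulated in two separate programs: multinomial outcomes, week 4/8 imputation, the plan's allocation formula, a first look at 100 patients with 12-week data, then 13-week looks and a linear ramp. Entries are early / late / final rule met on complete data.

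| Setting | Scenario 2 | Scenario 3 | Scenario 1 (null) |
|---|---|---|---|
| Table 6 | .777/.021/not given | .923/.016/not given | .055/.006/not given |
| A: week 4 and 8 independent, looks continue after full enrolment, prior 1/3 | .801/.022/.725 | .925/.014/.875 | .049/.003/.027 |
| B: no looks after full enrolment | .734/.080/.710 | .890/.045/.862 | .039/.007/.032 |
| C: week 4 and 8 identical | .793/.025/.711 | .937/.014/.872 | .050/.003/.029 |
| D: prior 1 | .793/.019/.705 | .925/.014/.873 | .034/.005/.022 |
| E: second program, no looks after full enrolment | .732/.068/.695 | .876/.058/.863 | .043/.006/.035 |

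A–D used 1,500 trials per cell and E 1,000, with a standard error of about 1 point. Early plus late comes within about 3 points of Table 6 in every row; the final-rule figures do not. Further runs gave .696–.744 and .857–.877.

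Early stops that fell to .925 or below on complete data:

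- Scenario 2: from 146/1201 = 12% (A) to 156/1101 = 14% (B).
- Scenario 3: from 95/1387 = 7% (A) to 118/1405 = 8% (C).
- Null: from 21/59 = 36% (B) to 37/74 = 50% (A). E gives (.043 − .029)/.043 = 33%.

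In A–D, 1,046 of 10,197 early stops in Scenarios 2 and 3 slipped, with a median probability of about 0.90. The leading drug changed in one.

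**Look interval**

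Four-week looks, as Step 4 reads, give mean N of 269 and 231. Thirteen-week looks give 286–289 and 253–255. Table 6 has 298 and 266, so it lies nearer the 13-week schedule.

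**The case against.** On duration, the column is not defined, and the Statistical Model section speaks of stopping the trial at the crossing, so time to stopping is a defensible reading. No sample size, threshold or error rate depends on the extra weeks. That last point stands. The reading itself helps only in part: the text calls the figures average lengths, and the same column includes follow-up for full-length trials, so it mixes two clocks. Also, 87 and 79 add a full 12 weeks to every early stop. A crossing after enrolment has ended needs less, and simulated differences were 8.7–9.1 and 10.4–10.7 weeks against 9.3 and 11.1.

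On power, the plan states openly that early success means stopping early, and Table 6 shows the components. The 80% and 94% are therefore disclosed, not miscalculated.

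A reader might infer that the plan has no criterion for the confirming analysis. The documents do not support this: the design summary sets .925 for the final analysis, which naturally covers the analysis run once all enrolled patients have data. Nor can the gap be closed by reading confirmation as the same drug still leading, because that would replace the written rule.

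The re-simulated figures rest on inputs the plan does not give: ramp shape, week 4/8 correlation, looks after full enrolment and the exact prior. They also miss Table 6 in places. Mean N runs about 3–5% low in Scenarios 2 and 3, and without looks after full enrolment the early/late split fits worse.

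**Conclusion.** **Duration: wrong as written, high confidence.** The lengths for Scenarios 2 and 3 are too short by at least 5.0 and 7.3 weeks with no ramp, from the documents' figures alone. They are too short by about 9 and 11 weeks when follow-up is added to the stated values, or slightly less if some stops occur after enrolment has ended. Scenarios 1 and 4 change by about 1 week.

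**Power: a narrower gap, moderate confidence in its size.** The stated 80% and 94% are chances of an interim crossing or late success. The chance of meeting the final-analysis rule is not reported. About 70–74% and 85–89% are illustrative values that cover all runs and their sampling error. The plan also does not say what is concluded from an early stop that ends at .925 or below.

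A reader might infer that the design is unsound or that Type I error is inflated. Neither follows. Under the final-analysis rule the null false-winner rate falls to about 2–3.5%, against the stated 6.1%, and the leading drug almost never changes. The null slip rate, about 36–50% by setting and 33% in the second program, comes from few stops and is illustrative only.

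**Minor.** The four-week repeat in Step 4 conflicts with the 13-week looks.

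**What to change.** 1. Restate Mean Trial Weeks, and the matching sentences, to include follow-up after early stops. Alternatively, label the column as time to stopping enrolment for early stops and give time to complete data beside it.
2. Rescore the existing simulations on the final-analysis rule. Report that success probability and the null false-winner rate beside the crossing-based figures, with the share of early stops that fall to .925 or below and the share in which the leading drug changes.
3. State under Bayesian Adaptive Design what is concluded when an early stop does not meet .925 on complete data, and fix this before data are seen.
4. Reconcile Step 4 with the 13-week schedule, and state which interval produced Table 6.

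The cost is one column, a sentence or two, and rescoring of simulation output; Step 5 already calls for a complete-data evaluation. The stated durations will look less favourable, and a lower power figure will probably stand beside the present one. No patients are added.

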## **D. Analytic Methods**

### Overview

The primary aim of this study is to determine which drug is most effective and most tolerable in producing pain relief. We will perform a prospective randomized comparative effectiveness adaptive design study with those who do not have diabetes and in whom no other cause for neuropathy has been found. We have an agreement from 40 sites to participate in the study and four drugs will be tested. In this design we will perform several interim analyses (interims) while controlling the overall Type I error rate.

The following sections focus on specific details of this design and detail how we determined power, sample size, and duration of this trial. Throughout we add information to help those less familiar with our design and analyses better understand what we did and plan to do with this study.

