**Table 5. Simulation scenarios.**

		Treatment			
		1	2	3	4
Scenario 1	Pr(Quit)	0.2	0.2	0.2	0.2
Eff: No Difference	Pr(Efficacy)	0.3	0.3	0.3	0.3
Quit: No Difference	Utility	1.025	1.025	1.025	1.025
Scenario 2	Pr(Quit)	0.3	0.25	0.15	0.3
Eff: Best and 2 nd Best	Pr(Efficacy)	0.3	0.4	0.5	0.3
Quit: Positive	Utility	0.925	1.050	1.225	0.925
Scenario 3	Pr(Quit)	0.3	0.25	0.15	0.3
Eff: One Strong Best	Pr(Efficacy)	0.3	0.3	0.5	0.3
Quit: Positive	Utility	0.925	0.975	1.225	0.925
Scenario 4	Pr(Quit)	0.2	0.4	0.4	0.2
Eff: One Strong Best	Pr(Efficacy)	0.3	0.3	0.5	0.3
Quit: Negative	Utility	1.025	0.825	0.975	1.025

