### Missing data:

Our primary statistical inference of the intervention measures (efficacy and medication quit rates) will label all patients with missing VAS data to be imputed as a failure. Therefore our study has valid type I error rates and has nominal confidence interval coverage properties as detailed in the proposal. A patient that is enrolled and randomized (note: after signing the consent form) into the study will either continue to take the randomly assigned pain medication (quit=0) or discontinue (quit=1). Among the patients that continue the pain medication, and have follow-up VAS outcomes, that patient will either drop their VAS pain score by ½ or better (efficacy=1) or they will not (efficacy=0). Among the patients that discontinue treatment of assigned pain medication, or having missing VAS values, they will automatically be recorded as non-efficacious (efficacy=0). Patients that are lost from the study will be considered to have discontinued treatment (quit=1, efficacy =0). The rule above implies that missing data will result in an imputed failure (and hence there are no missing primary outcomes). The primary inference in our study automatically addresses MD-3 of the PCORI Methodology Standards. Note: our secondary statistical inference of the intervention measure of reported VAS changes will be conducted using Bayesian mixed-effect model repeated measures (MMRM) where missing data will be addressed using multiple imputation.

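### Scenario 4's 12% power is the rate of falsely naming a sole best drug when two drugs tie, and Type I error is shown only for a four-way tie

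*Combined protocol and SAP*

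**What the plan says.** Combining Endpoints and Statistical Model define the best drug as the arm with maximum utility, U = 0.75E + 1 - Q. A trial succeeds when the posterior probability that one arm is best exceeds 0.925.

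Power, Sample Size, and Trial Duration treats power as the probability of success. For Scenario 1, with all four drugs equal, it says that success "actually reflects our Type I error rate", and it reports 5.5% early plus 0.6% late. For Scenario 4 it describes one drug that is strongly best on efficacy but has a higher quit rate, and concludes "Thus this simulation had 12% power".

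Two other places make general claims. The Overview of Analytic Methods promises several interim analyses "while controlling the overall Type I error rate". Missing data says "Therefore our study has valid type I error rates".

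On coverage, the power section says "we include all possible combinations in Table 5, ordered from most to least power". Table 5 contains four scenarios. Its fourth is labelled "Quit: Negative", a pattern that Table 4 explains as "Most efficacious drug has highest quit rate".

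After an early stop, Bayesian Adaptive Design says "we will confirm this finding with a subsequent analysis and evaluation after all data from all enrolled patients are obtained".

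**The concern.** Power is the chance of reaching a correct conclusion. If two drugs share the highest true utility, no sole-best conclusion is correct, and power to reach one is undefined. The plan applies this reasoning when four drugs tie and drops it when two tie.

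The trial's main conclusion is that one drug is best. A reader of Table 6 would take 11.5% as weak power in an awkward scenario, when it is the chance of declaring one winner between two equally good drugs. The reader would also take 6.1% as the trial's error rate, although the plan's own table holds a rate almost twice as high under another tie. Since the drugs may well be similar in pairs, partial ties are a plausible truth for this trial.

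**Working it through.** **1. Scenario 4 utilities** (Table 5 rates, U = 0.75E + 1 - Q)

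- T1 and T4: 0.75 × 0.30 + 1 - 0.20 = 1.025
- T2: 0.75 × 0.30 + 1 - 0.40 = 0.825
- T3: 0.75 × 0.50 + 1 - 0.40 = 0.975

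These match Table 5. T1 and T4 tie. T3, the strong best on efficacy, ranks third.

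**2. The plan's 12%** (Table 6, probability that each drug wins)

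- Sum: 0.053 + 0.000 + 0.011 + 0.051 = 0.115, which the text rounds to 12%.
- Names a tied-best drug: 0.053 + 0.051 = 0.104.
- Names an inferior drug (T3): 0.011.

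**3. Is it distinguishable from Scenario 1?** With 1000 simulated trials, exact 95% intervals are 9.6-13.6% for 0.115 and 4.7-7.8% for 0.061. The difference is 0.054. Its standard error is √(0.115 × 0.885/1000 + 0.061 × 0.939/1000) = 0.0126, so the difference is about 4 standard errors. The 6.1% is compatible with 0.05 and is not disputed.

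**4. How many planned combinations have no unique best?** Table 4 gives 5 efficacy × 3 quit patterns = 15. Applying the utility to each leaves five without a unique best:

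- No Difference on both endpoints (all four tie).
- The Negative quit pattern with No Difference, Best and 2nd Best, One Strong Best, or One Modest Best efficacy. T1 and T4 tie at 1.025 in each.

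All Different × Negative is not a tie, because T1 alone leads at 1.100. Table 5 shows 4 of the 15 combinations and 2 of these 5.

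**5. The Negative pattern.** Table 4 gives T3 a quit rate of 0.60; Table 5 uses 0.4. Quit and efficacy are exclusive categories of one multinomial, so E + Q cannot exceed 1. With 0.60 and efficacy 0.50 the sum is 1.10. That is infeasible in three Negative combinations: Best and 2nd Best, All Different, and One Strong Best. The T1-T4 ties do not depend on T3's value, but two of the five tied combinations are feasible only with a lower T3 quit rate such as Table 5's 0.4.

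**6. Size in the unreported ties.** The design was simulated in three separate runs (1000, 1000 and 600 trials per scenario).

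- From the plan: the longitudinal transition priors and early-outcome probabilities, the adaptive allocation formula from 80 patients, a first look at 100 patients with 12-week data, looks every 13 weeks, a maximum of 400, and 4.2 patients/week.
- Assumed: the prior read as Dirichlet(1/3, 1/3, 1/3), and a linear 8-week accrual ramp.

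Each cell gives the percentage crossing 0.925 at any look or at the end / the percentage above 0.925 at the final analysis. The Negative rows use T3 quit 0.4.

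| Truth | Table 6 | Run 1 | Run 2 | Run 3 |
|---|---|---|---|---|
| Scenario 1 | 6.1 | 5.5 / 3.0 | 4.6 / 2.9 | 4.7 / 2.2 |
| Scenario 4 | 11.5 | 9.8 / 5.8 | 11.6 / 8.1 | 12.0 / 7.5 |
| No Difference × Negative | not given | 23.6 / 16.4 | 25.6 / 17.3 | 22.7 / 14.7 |
| One Modest Best × Negative | not given | 17.9 / 11.3 | not run | 17.7 / 12.0 |
| Best and 2nd Best × Negative | not given | 7.9 / 4.5 | not run | 8.7 / 5.0 |

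Crossing rates for Scenarios 2 and 3 were 81.6% and 94.1% in run 1 and 80.3% and 92.5% in run 2, against 79.8% and 93.9% in Table 6. All crossing rates are within 2 points of Table 6; the final-analysis rates are lower. This suggests that Table 6 counts an early stop as success without the later confirmation.

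In run 2, No Difference × Negative split as 0.119 for T1 and 0.137 for T4, with none for T2 or T3.

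Two sensitivities from run 1:

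- With T3 quit 0.60, No Difference × Negative gives 27.7 / 19.7 and One Modest Best × Negative 28.2 / 19.6.
- With the four-week repeat in Simulation Algorithm, Scenario 1 gives 7.4 / 3.2, Scenario 4 gives 14.9 / 7.0, and No Difference × Negative gives 26.0 / 14.2 (0.4) or 34.8 / 22.3 (0.60).

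**The case against.** The strongest reply is that nothing is miscalculated or hidden. The plan defines power as probability of success, 12% is that quantity, Table 5 prints the tie and Table 6 prints each drug's wins. This is true, and the fault lies in the label and in the absence of any partial-tie error assessment. But the same definition would make Scenario 1's 6.1% power, and the plan calls that Type I error.

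A second reply is that naming one of two tied-best drugs harms no patient on the plan's own utility: 0.104/0.115 = 90% of Scenario 4's declarations name a drug that none beats. This also stands, and the simulated rates for other ties must not be read as wrong-drug rates. The false part is that the winner is sole, which is what the trial would announce.

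Third, the power section ties its Type I statement to Scenario 1, and the Missing data sentence points back to the proposal's details. So the Overview is the only wholly unqualified claim. That narrows the rewording but does not remove the need for it.

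Fourth, the added rates rest on an assumed ramp, and requiring confirmation brings Scenario 4 down to about 6-8%. The four-week figure for Scenario 4 (14.9%) lies above the interval around Table 6's value (9.6-13.6%), so 13-week looks fit better and the four-week results are secondary. Both points are fair. They are reasons for the sponsor to report its own values on both bases.

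**Conclusion.** The point holds. From the plan's own figures, Scenario 4 has no unique best drug, and its 0.115 is a false sole-best declaration rate: 0.104 tied-best and 0.011 inferior. It is about 1.9 times the 0.061 shown for the global null. Control of Type I error is demonstrated only for the four-way tie. None of this depends on simulation.

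The size in the unreported ties does rest on simulation under the stated assumptions. With 13-week looks and T3 quit 0.4, No Difference × Negative gives about 23-26% crossing and 15-17% at the final analysis. One Modest Best × Negative gives about 18% and 11-12%. Best and 2nd Best × Negative gives about 8-9% and 5%, below Scenario 4. For runs of 1000 trials, Monte Carlo error is about ±1.4 points at 5.5% and ±2.8 points at 28%.

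**What to change.** 1. Relabel Scenario 4's 0.115 as a false sole-best declaration rate, and give the 0.104/0.011 split in the text.
2. In the Overview, the power section and Missing data, limit the Type I statements to the global null and state 6.1%.
3. Make Tables 4 and 5 agree on the Negative quit pattern, using values for which E + Q does not exceed 1.
4. Report the omitted combinations, or at least the three unreported T1-T4 ties. For each, give the crossing rate, the rate at the final analysis and the split between tied-best and inferior drugs, and state the largest value found.
5. Run these at the look interval the trial will use, and reconcile the 13 weeks in Bayesian Adaptive Design with the four weeks in Simulation Algorithm.

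The cost is text changes and a few extra rows from existing simulation code. The stated error rate becomes less favourable. Changing the 0.925 threshold would trade against power and is not part of this fix.
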